## Protocol

Title: Can You Reduce Diabetes Symptomatology by Becoming Your ‘Best Possible Self’?: The Role of Stress and Resilience.

### Research Question

How does the ‘Best Possible Self’ Task influence stress and resilience when used as a diabetes prevention tool?

### Background

Diabetes mellitus continues to be a global burden and it affects millions of people around the world (Bommer et al., 2017). Prevalence figures from 2015 revealed that approximately 5 million adults in England alone were at high risk of developing type 2 diabetes specifically (Public Health England, 2016), a form of the disease that is largely preventable via lifestyle changes (Klein, Sheard, Pi-Sunyer, Daly, Wylie-Rosett, Kulkarni, & Clark, 2004). Typically, education interventions are utilised in efforts to promote awareness and generate behavioural change prior to formal diagnosis (Lian, McGhee, Chau, Wong, Lam, & Wong, 2017; Roberts, Barry, Craig, Airoldi, Bevan, & Greenhalgh, 2017) but this is not always enough to motivate individuals to act (Horgan, Davies, Findlay-White, Chaney, & Voates, 2017). Research has demonstrated that emotionality plays a significant role not only in lifestyle change but also in symptom management (Rasmussen, Smith, Maxson, Bernard, Cha, Agerter, & Shah, 2013). Experiencing mental illness, distress, or even just a high frequency of negative emotions can negatively influence dieting and exercising behaviours (Ciechanowski, Katon, & Russo, 2000), for example, increasing risk. However, novel findings have shown that experiencing positive emotions (such as happiness, optimism, interest, feelings of strength, etc.) can have the opposite effect and may help empower the individual to make the changes they need to improve their health (Garland, Fredrickson, Kring, Johnson, Meyer, & Penn, 2010). Interventions designed to foster positive emotions specifically are in development across psychology and have shown to improve mental as well as physical health outcomes (Chew, Vos, Heijmans, Metzendorf, Scholten, & Rutten, 2015). This has been supported by our own investigations whereby we discovered that one such “positive” intervention reduces certain diabetes symptoms regardless of the individual’s level of risk.

[figure not shown]
The positive intervention we have been using is an adapted version of the ‘Best Possible Self’ (BPS) task – a goal setting exercise that has shown to be effective in improving illness management and facilitating positive emotions (King, 2001). Its influence on diabetes symptoms is a novel finding, and with this study we are hoping to further investigate how it achieves this effect. According to the Stress Buffering Model of Physical Activity (Pressman & Cohen, 2005), psychological stress is the catalyst that triggers behavioural and physiological responses critical to health and positive emotions improve health by helping people to cope. The Broaden and Build Theory of Positive Emotions, meanwhile, suggests that this is because positive emotions allow people to build resilience (Fredrickson, 2001). Research around stress and resilience has shown these factors to be important not only in physical health of people with diabetes (Yi, Vitaliano, Smith, Yi, & Weinger, 2008) but for also decreasing illness symptomatology in non-clinical samples more generally (Steinhardt & Dolbier, 2008). As such, this proposed study aims to assess the role that stress and resilience may play in mediating the relationship between BPS and diabetes symptomatology.

### Hypotheses:

The ‘Best Possible Self’ task will increase resilience and alleviate stress in order to reduce symptoms of diabetes in a non-clinical sample.

[figure not shown]
## Methodology

See flowchart below:

## Analysis

A series of MANOVAs will be used to assess the influence of the BPS on diabetes symptoms over time and across groups. MANCOVAs will be used to control for diabetes risk. A mediation analysis will be conducted using the PROCESS software (Hayes, 2012) to assess whether the relationship between the BPS and diabetes symptoms is mediated by stress and resilience.

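### If groups are randomised and symptoms are measured before the task, a group contrast adjusted for baseline symptoms would usually be more precise than the planned repeated-measures MANOVA

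*Combined protocol and SAP*

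**What the plan says.** The symptom analysis takes two sentences of the Analysis section: "A series of MANOVAs will be used to assess the influence of the BPS on diabetes symptoms over time and across groups", and "MANCOVAs will be used to control for diabetes risk". Baseline symptoms are not named as a covariate, and the section does not say which term (group, time or their interaction) decides whether the task works. The Hypotheses section expects the task to "reduce symptoms of diabetes in a non-clinical sample". The Methodology section reads "See flowchart below", and the flowchart is not shown in the text available. The readable text therefore gives no allocation method, number of groups or measurement times. It also gives no sample size, SD or pre-post correlation.

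**The concern.** A hypothesis about reduction, tested with time and group as factors, points to the group-by-time interaction as the natural test. With one pre-task and one post-task wave, that interaction is the between-group difference in mean change. In a randomised comparison the change score subtracts the whole baseline value, although the data usually support subtracting only a fraction of it. The rest adds noise. Adjusting for baseline lets the data set that fraction.

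At stake is precision. The change contrast usually needs more participants for the same power, and it carries part of any chance baseline imbalance into the estimate. Diabetes risk as a covariate does not repair this: if risk correlates equally with symptoms at both waves and the SDs are equal, it cancels out of the change score.

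**Working it through.** **Inputs.** The form of the analysis and its single covariate come from the Analysis section. The plan has no figure to reproduce. Everything else is assumed: two equal randomised groups, one pre-task and one post-task wave, two-sided 5% tests, pre-post correlation r from 0.5 to 0.9.

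**Large-sample variances.** Take pre-task SD 1 and post-task SD q.
- Change contrast: proportional to 1 + q² − 2rq, which is 2(1 − r) when q = 1.
- Baseline-adjusted contrast: proportional to q²(1 − r²).
- Change minus adjusted: (1 − rq)², never negative, and zero only when rq = 1.
- With q = 1 the ratio of adjusted to change is (1 − r²)/(2(1 − r)) = (1 + r)/2.

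**With diabetes risk in both models**, q = 1, and risk correlating a with pre-task and b with post-task symptoms: the change variance is 2(1 − r) − (b − a)², and the adjusted variance is 1 − (r² − 2abr + b²)/(1 − a²). For a = 0.3, b = 0.1, r = 0.9 these are 0.20 − 0.04 = 0.16 and 1 − 0.766/0.91 = 0.158, ratio 0.99.

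Variance ratio, adjusted to change:

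| Setting | r = 0.5 | 0.7 | 0.8 | 0.9 |
|---|---|---|---|---|
| Equal SDs | 0.75 | 0.85 | 0.90 | 0.95 |
| Post SD 1.2 × pre | 0.87 | 0.97 | 0.997 | 0.98 |
| Post SD 0.8 × pre | 0.57 | 0.63 | 0.64 | 0.61 |
| Risk in both, a = b = 0.3 | 0.73 | 0.84 | 0.89 | 0.95 |
| Risk in both, a = 0.3, b = 0.1 | 0.78 | 0.89 | 0.94 | 0.99 |

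Example for the second row at r = 0.5: 1.44 × 0.75 = 1.08 against 1 + 1.44 − 1.2 = 1.24, ratio 0.87.

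**Cost of estimating the slopes.** With p baseline covariates, N participants in total and equal SDs, the ratio becomes (1 + r)/2 × (N − 3)/(N − p − 3). It reaches 1 at r = 1 − 2p/(N − 3):
- N = 40, p = 3: 1 − 6/37 = 0.84
- N = 40, p = 1: 1 − 2/37 = 0.95
- N = 100, p = 3: 1 − 6/97 = 0.94
- N = 100, p = 1: 1 − 2/97 = 0.98

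**Power, change versus adjusted**, equal SDs, risk not modelled. The first row uses the non-central t. The other two are simulations of 40,000 trials per cell; the three scores correlate 0.5 with one another.

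| Setting | r = 0.5 | 0.7 | 0.8 | 0.9 |
|---|---|---|---|---|
| One score, 50/arm, effect 0.4 SD | 51% v 63% | 72% v 79% | 88% v 91% | 99% v 99% |
| One score, 20/arm, effect 0.6 SD | 46% v 56% | 67% v 72% | 83% v 86% | 98.6% v 98.7% |
| Three scores jointly, 20/arm, effect 0.6 SD | 44% v 52% | 66% v 69% | 84% v 85% | 99.2% v 98.9% |

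Both estimators averaged the true effect in every simulated cell.

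**Chance imbalance.** At 50 per arm the SD of the baseline difference is √(2/50) = 0.2, so a difference beyond 0.2 SD arises in 32% of randomised trials (53% at 20 per arm). Given equal SDs and an imbalance of 0.2 SD, the change contrast shifts by (1 − r) × 0.2 = 0.10, 0.06, 0.04, 0.02 SD at the four values of r. The adjusted contrast does not shift.

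**The case against.** **The conditions cannot be verified.** No readable section mentions randomisation or a pre-task symptom measure. Repeated measurement is implied, but a pre-task wave is not confirmed. This stands, and it is why the point is conditional. The unseen flowchart is not itself a fault of the plan.

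**The deciding test is inferred.** A series of MANOVAs could mean one analysis per wave, or several follow-up waves. The figures above belong to the two-wave design and do not carry over. The direction does hold in large samples. A post-task-only comparison has adjusted-to-unadjusted variance ratio 1 − r². With two or three follow-ups averaged, equal correlation between all waves and r of 0.3 to 0.7, the over-time contrast has 1.25 to 2.11 times the variance of the adjusted one.

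**A reader might infer that the planned MANOVA is always less precise.** The calculations do not support that. With three scores and 20 per arm, the joint MANCOVA loses above r of about 0.84. With a post-task SD 1.2 times the pre-task SD, little is gained from r = 0.7 upwards. The sample size is not in the readable text, so these cases cannot be set aside.

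**A reader might also infer bias.** Under randomisation both contrasts are unbiased on average.

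**The symptom test is not the main question.** The Research Question and Background centre on stress and resilience as mediators, and the Background reports the symptom effect as already found. This stands and lowers the priority.

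**Conclusion.** The point holds in its conditional form, as an optional efficiency improvement. If groups are randomised and symptoms are measured before the task, adjusting for baseline symptoms usually beats the change-score contrast. With equal SDs and large samples, the gain is worth about 25%, 15%, 10% and 5% of participants at r = 0.5, 0.7, 0.8 and 0.9. A larger post-task SD or a changing link between risk and symptoms reduces it; a smaller post-task SD increases it. It is near nil at high r and can reverse for a joint MANCOVA in small groups. All values of r, SD, sample size and effect are assumptions. The algebra is firm; whether it applies to this study depends on the flowchart.

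**What to change.** Check the flowchart. If it shows randomised groups and a pre-task symptom measure, state in the Analysis section that the conclusion about the task's effect on symptoms rests on the between-group contrast in post-task symptom score(s), adjusted for the baseline value of the same score(s) and for diabetes risk. When groups are small, use ANCOVA with one baseline covariate per score; keep a joint MANCOVA with all baseline scores for larger groups.

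Keep diabetes risk in the model. If it were dropped and it predicted change strongly, the ranking could reverse: at r = 0.7, with risk correlating 0 with pre-task and 0.5 with post-task symptoms, the risk-adjusted change contrast has variance 0.35 against 0.51 for a baseline adjustment without risk.

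If groups are not randomised, do not make this switch for precision. The two contrasts can then estimate different quantities: with equal SDs, a systematic baseline difference of 0.2 SD separates them by 0.10, 0.06, 0.04 and 0.02 SD at the four values of r. If there is no pre-task symptom measure, the point lapses.

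The cost is a change of wording, with no new data if symptoms are already collected before the task, and one degree of freedom per baseline covariate.

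### Does the series of MANOVAs and MANCOVAs need a named deciding test, error control and signed follow-up before it can answer the symptom question?

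*Combined protocol and SAP*

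**What the plan says.** The readable analysis plan is three sentences. On symptoms it says "A series of MANOVAs will be used to assess the influence of the BPS on diabetes symptoms over time and across groups". On adjustment it says "MANCOVAs will be used to control for diabetes risk". The third sentence plans a PROCESS analysis "to assess whether the relationship between the BPS and diabetes symptoms is mediated by stress and resilience".

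The Hypotheses section is directional: the task "will increase resilience and alleviate stress in order to reduce symptoms of diabetes in a non-clinical sample". The Background section reports that the team's earlier work found an intervention that "reduces certain diabetes symptoms regardless of the" individual's risk level, and says of the task: "Its influence on diabetes symptoms is a novel finding".

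The Methodology section is a flowchart that is not shown. It may define the groups, time points and symptom scales, so nothing here counts their absence against the plan.

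**The concern.** The hypothesis says symptoms will fall. The planned tests are omnibus tests, which show only that groups or times differ on some combination of scales. The Analysis section does not single out the group-by-time effect, does not choose between the adjusted and unadjusted models, gives no error rule across the series, and describes no step that would identify the scales that changed or their direction.

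The earlier effect covered only some symptoms, and those are not named, so a partial pattern is plausible. With a partial or mixed pattern, the choice of scales and model to emphasise could be made after the data are seen, and a scale could be called reduced by chance. A fall shared by all groups could also be credited to the task if the main effect of time were read as a treatment effect.

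**Working it through.** The plan states no sample size, power, alpha or number of tests in its readable text, so there is no figure of its own to reproduce. The illustrations below assume 5% per test, two groups of 50 (30 to 100 where a range is given), six symptom scales, and correlations of 0.3 to 0.5 between scales. None of these values comes from the documents.

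**1. Direction.** For two groups the MANOVA statistic is T² = [n₁n₂/(n₁+n₂)] d′S⁻¹d, where d is the vector of mean differences and S the pooled covariance matrix. Replacing d by −d leaves T² unchanged. In a simulated data set, p was 0.0399 before and after every sign was reversed. With all six scales 0.5 SD lower (correlation 0.3) the test rejected in 80.6% of runs; with all six 0.5 SD higher, in 81.0%. In none of the latter rejections was any scale significantly lower. The omnibus test is blind to direction, but the means are not.

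**2. Error across the series.** For m independent tests the chance of at least one false rejection is 1 − 0.95^m.
- m = 2: 1 − 0.9025 = 9.75%.
- m = 4: 1 − 0.8145 = 18.55%.

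These tests share outcomes and are correlated. Simulation with no true change and correlation 0.5 between scales (four or six scales) gives:
- two MANOVAs: 9.3% to 9.7%;
- two MANOVAs, each with its MANCOVA: 10.4% to 11.4%;
- one MANOVA with its own MANCOVA: 5.3% to 6.4%.

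Adding the risk-adjusted version therefore costs little. The figures near 10% need a second MANOVA that the text does not specify, and a rule that any rejection is a success, which the text does not state.

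**3. Falsely named scales.**
- *Nothing changes.* At correlation 0.3 the omnibus test rejected in 5.0% of runs, and in 51.5% of those rejections no scale was significantly lower. Unadjusted follow-up therefore names a reduced scale in 0.050 × (1 − 0.515) = 2.4% of trials.
- *One scale truly falls by 0.5 SD.* Unadjusted follow-up also names an unaffected scale in about 8% of trials (5.8% to 9.9% at 30 to 100 per group). With Holm it is about 2%.
- *One scale rises by 0.5 SD and none falls.* The omnibus test rejects in 50% to 64% of trials. A reduction is then named in about 8% of trials unadjusted and about 2% with Holm.

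**4. Which effect.** With change scores falling equally by 0.4 SD in both groups (correlation 0.3), the time effect rejected in 99.9% of 4,000 runs and group-by-time in 5.8% (nominal 5%). The choice of effect can settle the conclusion. But the plan asks about the task's influence "over time and across groups", and the effect that uses both parts of that phrase is group-by-time.

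**5. What a written rule would gain.** Take a rule that requires a significant omnibus test and then a Holm-adjusted fall on a named scale. Its power to claim any reduction, against Holm alone, is:

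| True pattern | Correlation | Gated Holm | Holm alone |
|---|---|---|---|
| All six fall 0.4 SD | 0.3 | 57% | 69% |
| All six fall 0.4 SD | 0.5 | 42% | 61% |
| One falls 0.5 SD | 0.3 | 35% | 43% |
| One falls 0.5 SD | 0.5 | 39% | 43% |

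The gate barely changes false naming when one scale falls (2.2% against 2.4%, and 1.9% against 2.0%). Against a single total score with falls of 0.4 SD, gated Holm has 20% to 21% power against 6% to 7% if one of six scales falls, but 42% to 57% against 74% to 87% if all six fall. No rule is best across the plausible patterns.

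**The case for a change.** The strongest case for a change is that the hypothesis is directional, the effect reported in the Background section covered only some symptoms, and an omnibus test cannot support a claim about particular scales. MANOVA controls error only within one test, not across the series or in later scale-by-scale tests. The mediation model does give signed coefficients, but the plan does not name it as the follow-up. Decision rules belong in the Analysis section, which is readable and silent, so the missing flowchart is not a full answer. The remedy would be wording only.

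Much of this stands. The omission is real, and the flowchart is unlikely to hold an error rule. What does not stand is the step from omission to defect. The larger figures need assumptions the plan does not make: that any rejection counts, that follow-up is unadjusted, or that a time effect is credited to the task. The remedy is not neutral either. The Research Question concerns stress and resilience, the Background ends by making their mediating role the aim, and the hypothesis is worded through them. Making a symptom test the sole decider would choose the primary question for the sponsor and leave the mediation analysis unranked. Gating Holm behind the omnibus test would also give up power, as shown above.

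**Conclusion.** No change is called for. The plan leaves a decision rule unwritten; it does not state a rule that gives a wrong answer. An analyst following it would test group-by-time, read direction from the means and look at the individual scales.

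Under the assumed inputs (5% per test, 50 per group, six scales, correlations 0.3 to 0.5), the false naming of a reduced scale is about 2% when nothing changes. It is about 8% when another scale truly moves by 0.5 SD and follow-up is unadjusted. Reporting both the adjusted and unadjusted versions of one model takes a 5% error rate to 5.3% to 6.4%. These are illustrations only, since the number of tests, scales, participants and the alpha are not in the readable text. Readers of the results should treat scale-level claims with the usual caution about multiple tests.

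### The mediation model that tests the study's hypothesis names no covariate; adding baseline symptoms and diabetes risk is a cheap, partial guard against reporting mediation that is not there

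*Combined protocol and SAP*

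**What the plan says.** Mediation is the purpose of the study. The Background section states that "this proposed study aims to assess the role that stress and resilience may play in mediating the relationship between BPS and diabetes symptomatology", and the Hypotheses section predicts that the task works on symptoms by raising resilience and lowering stress.

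The Analysis section gives this test one sentence. It opens "A mediation analysis will be conducted using the PROCESS software" and goes on "to assess whether the relationship between the BPS and diabetes symptoms is mediated by stress and resilience". That fixes the software, the exposure, two mediators and the outcome. It does not say which covariates enter, or whether post-task or change scores are used.

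Two other statements in the same section matter. Adjustment for risk is attached to a different analysis: "MANCOVAs will be used to control for diabetes risk". The MANOVAs are meant "to assess the influence of the BPS on diabetes symptoms over time and across groups", which implies a symptom score before the task. The Methodology section is a flowchart that cannot be seen in the available text.

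**The concern.** Even if the BPS task is randomised, stress and resilience are not. The path from mediator to symptoms is therefore an association, open to confounding like any observational one. The model can declare mediation with no mediator effect if four things hold together:

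1. Post-task scores are analysed.
2. No covariate is entered.
3. Stress or resilience was already correlated with symptoms.
4. The task shifts the mediator.

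The study expects the fourth. The Background makes the third plausible without sizing it: "Research around stress and resilience has shown these factors to be important not only in physical health of people with diabetes", and also "for also decreasing illness symptomatology in non-clinical samples more generally". It also says "Experiencing mental illness, distress, or even just a high frequency of negative emotions can negatively influence dieting and exercising behaviours" and ties this to higher risk, which makes diabetes risk a plausible common factor. The first two are neither stated nor ruled out.

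At stake is the reading of a positive result. Without adjustment, it could not separate a task that lowers symptoms through stress or resilience from a mediator that was merely related to symptoms beforehand.

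**Working it through.** The readable text states no sample size, power or correlation, so there is no figure of the plan's to reproduce. **Every input below is an assumption.**

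**Set-up.** Two equal arms; the task shifts the mediator by 0.5 SD; the true mediator effect on symptoms is 0; diabetes risk correlates 0.3 with mediator and symptoms. Two data models:
- A: each score is a stable trait (60% of variance) plus independent noise. r is the trait correlation between mediator and symptoms, so the observed correlation is 0.6r.
- B: post = 0.7 × baseline + noise with variance 0.51. r is the baseline correlation, so the post-task correlation is 0.7 × 0.7 × r = 0.49r.

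**Hand check, no covariate, one mediator.** Mediation is declared roughly when both paths are significant at two-sided 0.05. Path a: z = 0.5/√(2/n). Path b: z = ρ√(N−3)/√(1−ρ²), with n per arm, N = 2n and ρ the within-arm correlation.
- 50 per arm, path a: z = 0.5/0.2 = 2.5, power 0.70.
- A, r = 0.1: ρ = 0.06, z = 0.59, power 0.09; product 0.06.
- A, r = 0.3: ρ = 0.18, z = 1.80, power 0.44; product 0.31.
- A, r = 0.5: ρ = 0.30, z = 3.10, power 0.87; product 0.61.
- A, r = 0.5, 100 per arm: z = 3.54 and 4.41, powers 0.94 and 0.99; product 0.94.

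**Simulation** (2,000 trials per cell, Monte Carlo interval for a×b). False-mediation rates in percent, A/B; – means not run:

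| Mediators, n per arm, r | No covariate | Risk only | Risk + baseline symptoms |
|---|---|---|---|
| One, 50, 0.1 | 6/4 | – | 4/3 |
| One, 50, 0.3 | 29/18 | 17/11 | 6/3 |
| One, 50, 0.5 | 59/45 | 52/37 | 19/3 |
| One, 100, 0.5 | 93/88 | 91/81 | 47/5 |
| Two, 50, 0.3 | 30/26 | – | 11/6 |
| Two, 50, 0.5 | 66/56 | – | 26/7 |
| Two, 100, 0.5 | 98/94 | – | 59/8 |

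The no-covariate column for A agrees with the hand check. With two mediators, either one counts as positive; with r = 0 the no-covariate rate is 5% to 9%. With 30 per arm and one mediator, the no-covariate rate is 6/5% at r = 0.2 and 29/20% at r = 0.5. With no shift in the mediator it is 3% to 5%.

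**Why the fix is partial.** Leave risk aside and condition on baseline symptoms. In B the mediator-symptom covariance becomes 0.49r − 0.7r × 0.7 = 0, so the confounding goes. In A it becomes 0.6r − 0.6r × 0.6 = 0.24r, so some stays, because one baseline score measures the trait with error.

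**A second two-mediator simulation** (joint significance, stability slopes 0.6, baseline correlation 0.4) gives the same direction: 15.9% to 5.1%, 34.4% to 7.4% and 72.2% to 9.5% for 60, 100 and 200 participants in total. If baseline stress and resilience also act directly on later symptoms, the figures are 32.8% to 12.6%, 68.6% to 25.2% and 97.8% to 56.7%.

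**Shared post-baseline cause** (noise correlation 0.3, 50 per arm, one mediator), A/B:

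| r | No covariate | Risk + baseline symptoms | Plus baseline mediator | Change scores |
|---|---|---|---|---|
| 0.3 | 59/60 | 41/40 | 53/78 | 26/79 |
| 0.1 | 29/38 | 24/42 | 40/81 | – |

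A repeat at r = 0.1 gave 26/34% without covariates, 39% in B with the two covariates, and 37/79% with the baseline mediator added. Arithmetic for B at r = 0.1, ignoring risk, shows why. The unadjusted correlation is 0.049 + 0.51 × 0.3 = 0.202. Given baseline symptoms it is 0.153/√(0.9951 × 0.51) = 0.215. Given the baseline mediator as well it is 0.153/0.51 = 0.30. Adjustment removes noise but not the shared cause.

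**The case against.** The strongest reply is that the Analysis section is a short outline. It commits to neither an unadjusted model nor post-task scores, and the flowchart that would show arms, assignment, numbers and schedule is not visible. All of this stands. A reader might infer that the plan has chosen an unadjusted analysis, or that it lacks a design. The documents support neither: the text is silent on the first, and the flowchart is missing only from the available copy. Silence still matters here, because the section does specify control for risk, and does so for a different analysis.

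A second objection is that the proposed covariates do not always help. This also stands: the r = 0.1 shared-cause row shows no reduction in model B. It is tempting to go further and require baseline stress and resilience, or to rule out change scores. The results do not support either. Adding the baseline mediator raises the rate above no adjustment in both models at r = 0.1. Change scores beat every alternative in A at r = 0.3 but are worse than no adjustment in B. A shared cause, such as mood when questionnaires are completed together, is no less plausible than a stable trait link, and the documents size neither.

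Third, adjustment costs sensitivity. With a real mediator effect of 0.3 (r = 0.3, 50 per arm, one mediator), the positive rate falls from 57/58% to 40/38%. Part of the higher figure is spurious, but the loss is real.

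**Conclusion.** The concern holds in conditional form. The model that tests the aim and hypothesis is specified without covariates, while one suitable covariate is named and another implied in the same section. If it is run that way on post-task scores, with a prior mediator-symptom relation and a task effect on the mediator, false mediation can be well above the nominal level, and it becomes more frequent as the sample grows.

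The size for this study is unknown. The range from about 5% to over 90% reflects assumed correlations, shift and sample size, and no figure in the documents places the study within it. A reader might take the upper end as the expected error rate, or conclude that any positive result would be spurious; neither follows.

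Naming the two covariates is a better default than naming none when the confounding runs through baseline, and it makes little difference when the prior correlation is weak. Diabetes risk alone is not enough (52/37% at r = 0.5, 50 per arm). Both together leave about 3% to 19% at 50 per arm and up to 47% at 100 per arm with one mediator, and up to 26% and 59% with two. This is a cheap improvement, held with medium confidence.

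**What to change.** In the Analysis section:

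1. State that the PROCESS equations for stress, resilience and symptoms use post-task scores and include baseline symptoms and diabetes risk as covariates.
2. If baseline stress and resilience are collected, report a model that adds them and a change-score model as sensitivity analyses. Neither is best in all cases, and each can be worse than no adjustment under a shared post-baseline cause.
3. State that a positive result will be described as consistent with mediation, since no baseline covariate removes post-baseline confounding.

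The cost is two or three sentences and a few terms in the same software. The two main covariates need no new data, provided that symptoms are measured at baseline as the section implies. The price is the lower positive rate under real mediation given above, which should be accepted knowingly.
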